12.0 STATISTICAL CONSIDERATIONS

- 12.1 Primary and Secondary Endpoints: The primary endpoint of the Phase II study is to evaluate the efficacy of FTBI/BU/VP-16 with a targeted Busulfan dose of AUC 700-900 as a preparative regimen for allogeneic BMT in patients with advanced hematological malignancies (AML or ALL beyond second remission, in induction

failure, or in relapse; CML in blast crisis; and myelodysplasia, RAEB and RAEBIT). Secondary endpoints will include early and late toxicities of this regimen.

Efficacy will be estimated based on 2 and 5 year disease-free survival (DFS). The effects of cytogenetics, WBC at presentation, and number of courses of induction therapy to achieve remission will be evaluated as possible prognostic factors for relapse, DFS, and overall survival.

- 12.2 Sample size Estimation and Length of Accrual: A total of 50 patients with advanced malignancies and less than 50 years old (physiological age) will be accrued to this trial, so that in estimating the engraftment and relapse rates the maximum standard error will be 0.7. We expect to accrue approximately 10-12 patients per year so that this trial will require 4-5 years of completion.
- 12.3 If at any time the severe treatment related complication rate (e.g. severe VOD, interstitial pneumonia, neurotoxicity at day 100 post BMT) or regimen related mortality exceeds 20% with a high probability (i.e. >95%) then further accrual to the trial will be terminated. This would occur if the following numbers of events have been observed, monitoring after every set of 10 patients is accrued:

| Number of Patients Accrued | Number of Events Leading to Early Termination |
|-------------------------------|--|
| 10 | 5 |
| 20 | 8 |
| 30 | 11 |
| 40 | 14 |

12.4 **Statistical Analyses:** The rate of engraftment and median time to engraftment will be estimated, defined as time to ANC > 500 and platelets >20,000.

The Kaplan-Meier method will be used to estimate time to relapse, DFS, and overall survival, and 95% confidence intervals will be calculated using Greenwood's variance.

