APPENDIX X

Time points to grade toxicities and collect data.

Day 30 after PBSCT/BMT CTC form.

Day 31 – 100 CTC form and IBMTR booklet.

101 – 365 LT Follow up form.

Every year LT follow up form.

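### The stopping rule in Section 12.3 counts patients accrued rather than patients followed to day 100, so as written it stops later, and somewhat less often, than its table implies

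*Combined protocol and SAP*

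**What the plan says.** Section 12.3 is the only rule that closes the trial for toxicity. The criterion is that the severe complication rate or "regimen related mortality exceeds 20% with a high probability (i.e. >95%) then further accrual to the trial will be terminated". The complications are given by example: "severe VOD, interstitial pneumonia, neurotoxicity at day 100 post BMT". No window is given for regimen-related mortality.

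The test itself is a table with the column heading "Number of Patients Accrued" and limits of 5 events at 10 patients, 8 at 20, 11 at 30 and 14 at 40: "This would occur if the following numbers of events have been observed, monitoring after every set of 10 patients is accrued". The section opens differently: "If at any time the severe treatment related complication rate".

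Section 12.2 gives the pace: "We expect to accrue approximately 10-12 patients per year". Section 6.2 places the busulfan test dose on Day -14. Appendix X collects toxicity at day 30 and again later: "Day 31 – 100 CTC form and IBMTR booklet". Nothing limits the count to patients with day-100 follow-up, delays a look or holds accrual.

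**The concern.** The events in the numerator take up to day 100 to appear, while the denominator includes a patient from entry. The newest patients at a look are counted as if event-free for time they have not yet lived through. A fifth event among the first ten that falls just after the first look is not judged until 20 patients have been accrued, and then against a limit of 8. The reverse problem also exists. If the fifth event has occurred by the time patient 7 is in, the limit at 10 is certain to be met, yet the table lets patients 8-10 enter first. At stake is how many patients receive the regimen before the rule acts, if its toxicity is well above 20%.

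**Working it through.** **Inputs.** From the plan: null rate 20%, certainty above 95%, limits 5/10, 8/20, 11/30, 14/40 (12.3); 10-12 patients a year and 50 patients in all (12.2); first busulfan on Day -14 (6.2), so 14 + 100 = 114 days from first treatment to day 100. Assumed: evenly spaced entry, entry at first busulfan, and event times after transplant that are either uniform over days 0-100 or clustered early (exponential truncated at day 100, scale 30 or 15 days).

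**1. The plan's table.** The exact binomial tail P(X ≥ r | n, 0.20) is 0.033 for 5/10, 0.032 for 8/20, 0.026 for 11/30 and 0.019 for 14/40. With one event fewer it is 0.121, 0.087, 0.061 and 0.043. The first three limits are therefore the smallest counts with a tail below 0.05, and the fourth is one event stricter than needed. This treats every accrued patient as fully observed.

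**2. Incomplete patients at a look.** Entries are 365/12 = 30.4 to 365/10 = 36.5 days apart. Days since entry for the five newest patients are 0, 30, 61, 91, 122 at 12 a year and 0, 37, 73, 110, 146 at 10 a year. Four are short of 114 days in both cases. With a bare 100-day window the number is four at 12 a year and three at 10 a year.

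**3. What the first look sees.** Under uniform timing, a patient t days after entry has shown a share (t - 14)/100 of the eventual events, limited to 0-1. For the four newest patients that is 0, 0.16, 0.47, 0.77 at 12 a year and 0, 0.23, 0.59, 0.96 at 10 a year. With the six complete patients, the ten carry the information of about 7.4 to 7.8. With early clustering (scale 15) the shares at 10 a year are 0, 0.78, 0.98, 1.00, and the ten carry 8.6 to 8.8 over the two accrual rates.

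**4. Chance of stopping.** First-look values as written are exact sums over patients with event probability (true rate × share), except the 20% row, which is simulated. Complete-follow-up values are exact. Ever-stopping as written is simulated, with 40,000 trials per scenario. Ranges cover 10-12 a year and all the timings above.

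| True rate | First look, as written | First look, complete | Ever, as written | Ever, complete |
|---|---|---|---|---|
| 20% | 1-2% | 3% | 3-5% | 7% |
| 30% | 4-9% | 15% | 28-35% | 42% |
| 40% | 13-24% | 37% | 74-80% | 85% |
| 50% | 28-47% | 62% | 97-98% | 99% |

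**5. Mean patients treated.** Two changes must be kept apart. The first is complete follow-up alone: each row is judged when its last patient reaches day 100 and accrual is not paused. In 114 days three more patients enter (114/36.5 = 3.1; 114/30.4 = 3.7). With complete data the mean is 24.0 at a true rate of 40% and 15.4 at 50%, so it becomes 24.0 + 3 × 0.847 = 26.5 and 15.4 + 3 × 0.987 = 18.4. The second is to count continuously as well, and stop as soon as a row's limit is reached (simulated).

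| True rate | As written, uniform | As written, early | Complete follow-up alone | Continuous counting too, uniform |
|---|---|---|---|---|
| 40% | 30-31 | 27-29 | 26.5 | about 24 |
| 50% | 20-21 | 18-19 | 18.4 | about 15 |

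Under uniform timing at 50%, complete follow-up saves 2-3 patients and continuous counting a further 3-4. With early events, complete follow-up alone saves about 1-2 patients at 40% and essentially none at 50%.

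**The case against.** Four points can be made for the plan.

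- **The rule catches up.** Events missed at one look count at the next, so at high rates the rule nearly always stops in the end. This stands. A reader might infer that the rule stops far less often than its table implies. That fits the first look only; over all four looks the loss at 40% is about 5-11 points and at 50% about 1-2.
- **Pending patients are not blank.** A reader might also take 5 of 10 to mean 5 events in 6 observed patients. The text does not support this, because events that pending patients have already had are counted.
- **The opening words permit action at any time.** Read generously, a fifth event among the first ten could stop accrual between looks. But the only operative test is the table at 10, 20, 30 and 40, so the wording leaves a conflict and does not settle it.
- **There are other protections.** Section 7.2.2 changes the regimen on defined toxicity in 2 of the first 6 patients, and Appendix VIII sends certain adverse events and deaths to the IRB and the data safety monitoring board within 10 days. These soften the gap. Neither is a criterion for closing accrual, and the calculations above do not model them.

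**Conclusion.** The point holds in a limited form. The denominator does not match the day-100 window, 3-4 patients per look are incompletely observed, and the table has its stated property only with full follow-up. The direction is certain: the rule acts later and somewhat less often. The loss is large at the first look, moderate over the whole trial at true rates of 30-40%, and at 50% almost entirely a matter of delay. The size rests on even accrual at 10-12 a year and on event timing that the plan does not state; the earlier the events, the smaller the loss. The saving in patients should not be credited to follow-up alone, since at 50% most of it comes from continuous counting. The clash between action at any time and looks only at multiples of ten stands whatever the timing. Because this is the only accrual-stopping rule for toxicity, it should be corrected.

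**What to change.** Keep the four limits and rewrite Section 12.3 as follows.

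- Read each row as events among the first 10, 20, 30 or 40 patients, tallied continuously as they occur.
- End accrual as soon as any row's count is reached, whether or not that many patients have entered.
- Clear a row only when all its patients have reached day 100 or had an event. Accrual need not pause meanwhile.
- State the window that applies to regimen-related mortality, and reconcile the opening words with the table.
- Report the rule's stopping probabilities, with the event timing assumed.

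The cost is wording and a running tally. The day-30 and day 31-100 forms already collect the toxicities, but a live tally needs events that count under 12.3 to be notified when they happen. Appendix VIII does not require this for a known, non-fatal complication. At a true rate of 20% the chance of ever stopping rises from about 3-5% to about 7%, which is the level the table itself implies. Sample size and limits do not change.

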5.0 ELIGIBILITY CRITERIA

5.1 Inclusion Criteria

- 5.1.1 Patients with acute myelogenous or lymphocytic leukemia who are not in first remission or second remission i.e. after failing remission induction therapy or in relapse or beyond second remission, or patients with chronic myelogenous leukemia in blastic phase of the disease are eligible for the study. Patients with refractory anemia with excess blasts and in transformation will be eligible.
- 5.1.2 All candidates for this study must have a HLA (A,B,C,DR) identical siblings who is willing to donate bone marrow for marrow grafting. All ABO blood group combinations of the donor/recipient are acceptable since even major ABO compatibilities can be dealt with by various techniques. (Red cell exchange or plasma exchange). Peripheral blood stem cells or bone marrow can be used.
- 5.1.3 Prior therapy with VP-16 and busulfan is allowed.
- 5.1.4 Patients must be older than 16 and the upper age limit is physiological age of 50.
- 5.1.5 A cardiac evaluation with electrocardiogram and MUGA or echocardiogram is required in all patients. Patients must have an ejection fracture of greater than or equal to 50%.
- 5.1.6 Patients must have a serum creatinine of less than or equal to 1.2 or creatinine clearance $> 80\text{ml/min}$.
- 5.1.7 A bilirubin of less than or equal to 1.5. Patients should also have an SGOT and SGPT less than 5 times the upper limit of normal.
- 5.1.8 Pulmonary function tests including DLCO will be performed. FEV₁ and DLCO should be greater than 50% of predicted normal value.

5.1.9 The time from the last induction or reinduction attempt should be greater than or equal to 28 days.

5.1.10 Signed informed consent form approved by the IRB is required. The patient, family member and transplant staff physician (physician, nurse, and social worker) meet at least once prior to starting the transplant procedure. During this meeting all pertinent information with respect to risks and benefits to donor and recipient will be presented. Alternative treatment modalities will be discussed. The risks are explained in detail on the enclosed consent forms.

Revised 8/28/00

Revised 3/11/02

Revised 6/13/02

5.1.11 Patients with AML in first remission with poor risk cytogenetics (11q abnormalities, -7,-5, complex abnormalities i.e. > 3 abnormalities, 6;9 translocation and 3q abnormalities del (7q), del (5q), complex abn ≥ abnormalities, 9q, 20q, 21q, 17p, t(9;21)).

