5.2.4 Pregnancy

5.3 Donors

5.3.1 Any sibling donors who are histocompatible with the prospective recipient will be considered as a suitable donor.

5.3.2 Donors will be excluded if for psychological or medical reasons they are unable to tolerate the procedure.

5.3.3 Donor should be able to donate peripheral blood stem cells or bone marrow.

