6.2 Preparative Chemotherapy Regimen

Rev. 8/12/02

* Patient to sign consent form before starting Dilantin.

Rev. 11/8/01

Friday/Day -18

Begin dilantin 300mg/p.o. t.i.d. times 1 day, then 300mg/p.o./IV daily times 14 days.

Tuesday/Day -14

Admission or outpatient, dilantin blood levels will be checked and dose adjusted as needed to meet therapeutic range. Further adjustments if clinically indicated. Busulfan test dose administered at 6 a.m. as a single dose. The I/V dose is calculated as follows:

1. Body surface area (BSA) is calculated by the equation:

$$\text{BSA} = \frac{(\text{Actual body wt.(kg)} \times \text{height (cm)})}{3600}$$

Rev. 6/13/02

2. 22mg/m² I/V Busulfan will be given over 2 hours. Blood levels will be obtained with the first dose as per appendix 1 and will be performed at City of Hope.

Rev. 11/8/01

Wednesday/Day -13

Busulfan AUC will be calculated by standard methods available in the City of Hope Analytical Pharmacology Core Facility (APCF). The resulting AUC will be used to determine the dose required to achieve an AUC of 800 $\mu\text{M}^* \text{min}$ according to the following formula:

$$\text{Adj dose} = \text{Current dose} \times \frac{800\mu\text{M}^* \text{ min}}{\text{test dose AUC}}$$

Rev. 6/13/02

The maximum dose given will not exceed 32mg/m². There is no limit on dose reduction Busulfan dose will only be adjusted for AUC's <700 or >900 $\mu\text{M}^* \text{min}$.

Thursday/Day -12

The adjusted dose Busulfan dose will be given at 6 a.m. and blood levels will be repeated. Further dose adjustments will be performed if AUC >1000.

Friday/Day -11

Patient admitted to BMT or receive further dose of Busulfan in clinic.

Busulfan dosing restarted at 6 p.m. and is repeated every 6 hours for a total of 14 doses.

Tuesday/Day -7

Fractionated TBI will be given at 120 cGy per fraction for a total of 4 days for a total of 10 fractions for a total dose of 1200 cGy. See Appendix II.

Saturday/Day -3

VP-16 30mg/kg based on adjusted ideal body weight will be administered.

Tuesday/Day 0

PSC reinfusion/or BM infusion

See Appendix 3 for PSC Collection

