Appendix III

- 1). **G-CSF Administration to Donors:** All donors will receive G-CSF 10 µg/kg/day for 6 consecutive days from day -5 to day 0. G-CSF will be administered by a subcutaneous injection daily beginning 5 days prior to day 0 (defined as the day marrow would ordinarily be given).
- 2). **PBSC Collection:** Donors may undergo vein to vein collections or may receive an appropriate catheter inserted on or before day of the treatment regimen. Donors will receive -5 daily doses of G-CSF, 10µg/kg/day by subcutaneous injection commencing on day -5. These doses will be administered each day in the Outpatient Department or at home.

Treatment Schema for Donor

| Days | -5 | -4 | -3 | -2 | -1 | 0 |
|------------------|-----------|-----------|-----------|-----------|-----------|----------|
| G-CSF 10µg/kg/SQ | X | X | X | X | X | |
| PBSC Collection | | | | | X | X |

PBSC's will be collected in the afternoon of day -1 and reinfused on day 0. *If the collection on day -1 contains less than 5.0×10^6 CD34+ cells per kg recipient weight, a second collection will be performed the following morning and transfused on day 0.

If PBSC's cannot be collected by a vein to vein technique, a percutaneous Mahurkar catheter will be inserted.

General procedures will include the use of a standard apheresis machined (COBE Spectra, Lakewood Colo.), and processing up to 16 l of whole blood during the collection. (Refer to Standard Practice Manual for collection procedure).

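### Section 12.4 pools marrow and PBSC recipients into one engraftment rate and median, with no report of the graft mix or of results by source (minor, cheap to improve)

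*Combined protocol and SAP*

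**What the plan says.** Either graft is allowed at three places. Eligibility (5.1.2): "Peripheral blood stem cells or bone marrow can be used". Donors (5.3.3): "Donor should be able to donate peripheral blood stem cells or bone marrow". Day 0 in section 6.2: "PSC reinfusion/or BM infusion". I found no criterion for choosing between them, no expected proportion and no cap on either.

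Appendix III covers donor preparation. It opens with "All donors will receive G-CSF" and sets a CD34+ count (5.0 x 10^6 per kg of recipient weight) below which "a second collection will be performed the following morning and transfused on day 0". No cell-dose criterion is stated for marrow.

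Section 12.4 plans one analysis of engraftment: "The rate of engraftment and median time to engraftment will be estimated", "defined as time to ANC > 500 and platelets >20,000". It gives no breakdown by graft source. Section 12.2 names engraftment, with relapse, as a quantity whose precision justifies 50 patients. Section 12.1 lists candidate prognostic factors for relapse, DFS and overall survival: "The effects of cytogenetics, WBC at presentation, and number of courses of induction therapy to achieve remission will be evaluated as possible prognostic factors". Graft source is not among them. The Cox models in 12.4 cover those three outcomes and not engraftment.

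**The concern.** Engraftment is defined by neutrophil and platelet recovery, which may plausibly depend on the product infused. The protocol itself attaches importance to cell dose for one of the two products. If recovery does differ by source, a single rate and median average over two groups in proportions that the report would not show. The trial has one arm, so a reader can judge the figure only against other experience, and cannot do that well without knowing the mix. Section 12.2 expects accrual to take 4-5 years, so the mix could also change during the trial without being visible in a pooled figure.

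What is at stake is the interpretation of a descriptive estimate. No decision or hypothesis test in the plan uses it.

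**Working it through.** **1. The plan's own precision figure.** For a proportion, the SE is largest at p = 0.5: sqrt(0.25/n). With n = 50 this is sqrt(0.25/50) = 0.0707. Section 12.2 prints 0.7, which does not reproduce: it would need n = 0.25/0.7² = 0.51. A value of 0.07 corresponds to n = 0.25/0.07² = 51, so the printed figure is most likely a misplaced decimal point. The precision basis is therefore an SE of about 0.07 on all 50 patients pooled.

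**2. How far the mix can move the pooled median.** The documents give no split, no medians by source and no spread, so every input here is assumed, including which source is faster. Let w be the PBSC share and let recovery times be log-normal with log-SD 0.25. The pooled median t solves w·F_PBSC(t) + (1−w)·F_marrow(t) = 0.5.

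| Assumed medians, PBSC/marrow (days) | w = 0 | 0.25 | 0.50 | 0.75 | 1 |
|---|---|---|---|---|---|
| 15/15 | 15.0 | 15.0 | 15.0 | 15.0 | 15.0 |
| 15/18 | 18.0 | 17.2 | 16.4 | 15.7 | 15.0 |
| 15/21 | 21.0 | 19.5 | 17.7 | 16.2 | 15.0 |

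The end points only restate the inputs. The rows show that the shift can be no larger than the difference between sources, and is zero when there is none.

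**3. The rate.** The pooled rate is w·p1 + (1−w)·p2, so it also moves by at most the gap between sources. With assumed rates of 98% and 93%, an even split gives 0.5 × 0.98 + 0.5 × 0.93 = 0.955, and the full range is 5 points.

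**4. Precision by source.** The same SE formula on assumed splits of 50, with half-width 1.96 × SE and SE of the difference sqrt(0.25/n1 + 0.25/n2):

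| Split | Maximum SE, smaller / larger group | 95% half-width | SE of difference |
|---|---|---|---|
| 25/25 | 0.100 / 0.100 | 0.196 / 0.196 | 0.141 |
| 15/35 | 0.129 / 0.085 | 0.253 / 0.166 | 0.154 |
| 10/40 | 0.158 / 0.079 | 0.310 / 0.155 | 0.177 |
| 5/45 | 0.224 / 0.075 | 0.438 / 0.146 | 0.236 |

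These are worst cases at p = 0.5. Description by source is feasible. A comparison between sources would be imprecise at any split.

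**5. Graft source in the Cox models.** Section 2.0 reports a 40% relapse probability in the earlier phase I study. If that applied here, 50 × 0.40 = 20 relapses. Three named factors plus graft source make at least four, or about 20/4 = 5 relapses per factor, which is thin for a model that must include them all.

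**The case against.** The strongest case against the point is that engraftment decides nothing. Efficacy is DFS at two and five years, the listed secondary endpoints are toxicities, and the early-termination rule in 12.3 counts severe complications and regimen-related deaths. The plan sets no engraftment threshold and no historical comparison. That stands, and it is why the point is minor.

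The size is also assumed throughout. No section gives a difference in recovery between the grafts, and the blanket G-CSF statement in Appendix III may mean that PBSC was the usual source, in which case pooling would matter little. This stands too. However, that statement sits awkwardly with the marrow option elsewhere, and the passages need to be reconciled. Until they are, the mix is unknown, which is itself a reason to report it.

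Two stronger readings are tempting and should be resisted. A reader might infer that the engraftment result reflects graft mix and not the regimen. It does not: all patients have the same planned regimen, so the pooled figure reflects both. A reader might also infer that the Cox models ignore graft source and that this distorts the engraftment result. Those models do not analyse engraftment. The list in 12.1 is of possible factors and does not expressly exclude others, so graft source is unnamed, not ruled out. That graft choice follows disease risk or calendar time is conjecture, since no section says who chooses or why.

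**Conclusion.** The point holds in a limited form. Both grafts are permitted, 12.4 plans only pooled engraftment figures, and neither the mix nor results by source will be reported. The pooled estimate is valid for the patients treated but hard to interpret if recovery differs by source. The possible shift runs from nothing to the full difference between sources. Under the assumed 15/18-day medians, that is up to 3 days between all-PBSC and all-marrow. The documents do not allow a narrower statement.

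The omission does not threaten the primary analysis or any decision rule. It does not justify demoting the pooled estimate, whose precision is the basis for 50 patients, or forcing graft source into every Cox model. It is a cheap improvement of minor weight.

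**What to change.** In 12.4, keep the pooled engraftment rate and median time as the main estimate. Add the number of marrow and PBSC recipients, and the engraftment rate and median time with 95% CIs for each source. Label these descriptive, with no test between them.

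In 12.1, graft source may be listed as an exploratory candidate prognostic factor for relapse, DFS and overall survival. It need not enter every model.

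The cost is a few sentences and one table. Graft source is known for each patient at infusion, so no new data are needed. The drawback is a wide interval in the smaller group, which the text should acknowledge in advance. When 12.2 is next edited, the printed SE should be corrected to about 0.07.
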